**Table 1. Vaping Prevention Video Ads used in the Trial**

Condition	Ads	Prior recall n(%)
Real Cost – Health Harms	Epidemic: https://vimeo.com/325055700	198 (39.3%)
	Facts of Vaping: https://vimeo.com/413710792	189 (37.5%)
	Toxic Metals: https://vimeo.com/413711298	185 (36.7%)
Real Cost – Addiction	Hacked: https://vimeo.com/325055712	191 (37.7%)
	Vaping Mistake – Danny: https://vimeo.com/413711020	186 (36.8%)
	Nicotine addiction isn't pretty – Bathroom: https://vimeo.com/520033399	187 (37%)
Control	Definition: https://vimeo.com/514315064 Farming: https://vimeo.com/514315483 Manufacturing: https://vimeo.com/514315497	n/a

*Note.* Prior recall refers to reporting in the Visit 1 survey that participants had seen one or more of the ads in their assigned trial arm previously.

**Impact of The Real Cost Vaping Prevention Advertisements on
Adolescents**

Hypotheses and Analytic Plan

NCT #04836455

Version Date: 4/23/2021

Hypotheses

The goal of this study is to determine whether exposure to vaping prevention advertisements reduce susceptibility to vaping. The **primary hypothesis** is that participants who view *The Real Cost* vaping prevention advertisements will have lower susceptibility to vaping compared to those who view neutral vaping control ads at 3 week follow-up.

The investigators also aim to examine the impact of *The Real Cost* vaping prevention ads on a series of other vaping-related outcomes. **Additional hypotheses** are that, compared to exposure to neutral vaping ads, participants exposed to *The Real Cost* vaping prevention ads will report the following at 3-week follow-up:

- Lower susceptibility to vaping
- Higher health harm risk beliefs about vaping
- Higher addiction risk beliefs about vaping
- More negative attitudes toward vaping
- Less vaping
- Higher attention (assessed only at 2-week follow-up)
- Higher negative affect (assessed only at 2-week follow-up)
- Higher cognitive elaboration
- More social interactions

The investigators will also explore the effects of *The Real Cost* vaping prevention ads on cigarette smoking-related outcomes, compared to exposure to neutral vaping ads. There are **not have directional hypotheses** for the following outcomes:

- Susceptibility to smoking cigarettes
- Health harm risk beliefs about smoking cigarettes
- Addiction risk beliefs about smoking cigarettes
- Attitudes towards smoking cigarettes
- Cigarette smoking behavior

Finally, the investigators will explore whether health harms vaping prevention ads out-perform addiction *The Real Cost* ads. We have labeled this an exploratory activity because the study is powered to compare these ads to control ads but not to one another.

Primary analyses

The investigators will use a critical alpha of 0.05 in all statistical tests. Analyses of the primary and secondary outcomes will include all randomized participants according to the trial arm they were randomized to receive (i.e., intent-to-treat). The investigators will use multiple imputation to handle any missing data on predictors and full information maximum likelihood to handle any missing data on outcomes.

The investigators will report univariate and bivariate descriptive statistics for the primary and secondary outcomes.

For significance testing of the primary hypotheses, the investigators will compare those in *The Real Cost* trial arms (combined) to the control arm. The investigators will use latent curve models so that the investigators can model change in repeated measures over time. After establishing a linear growth trajectory for each latent construct with the intercept coded to be at the last time point, the investigators will regress the latent intercept and slope factors for each outcome on an indicator of random assignment to *The Real Cost* trial arms or to the control arm.

A significant effect on the intercept will indicate a main effect of treatment assignment on the mean level of each outcome at the last time point. A significant effect on the slope, if positive, will indicate that repeated viewing of the ads led to an increase in the difference across trial arms. If negative, it will indicate that the treatment effect diminished over time. As a secondary analysis, the investigators will examine whether there were significant differences in growth factor means as a function of assignment to the *The Real Cost* ad trial arms.

The investigators will also conduct the above analyses comparing those in the *The Real Cost* health harms trial arm to those in the *The Real Cost* addiction trial arm to explore whether there are differences across those trial arms.

The investigators will use a separate model for each of the study outcomes. To account for multiple comparisons, the investigators will use a Benjamini-Hochberg correction to maintain a 5% false detection rate.

Finally, the investigators will conduct exploratory moderation analyses on the primary outcome to examine whether the following variables moderate the impact of *The Real Cost* trial arms (compared to the control arm) on susceptibility to vaping: gender, age, race, Hispanic ethnicity, sexual orientation, parent's education, current vaper (vs. non-current vaper), and tobacco user in the household.

Sample size and power

The investigators plan to enroll 500 individuals per trial arm with the expectation that as many as 33% of participants will drop out of the study before week 3 follow-up. The investigators will use a FIML estimator so the investigators can retain all available data, including observed repeated measures from participants who go on to drop out of the study. With an estimated ICC=.7 (and thus a design effect of 2.4), the investigators have statistical power to detect an effect as small as Cohen's $d = .25$. This effect size is around the same magnitude as the effects observed with pilot data. The investigators expect that the effects will be larger than what is observed in pilot data because the latent variable approach will result in higher reliability measures.

Interim analysis

No interim analyses are planned.

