## Measures

At the first session (Visit 1), each participant reported vaping and smoking behaviors in the survey, then viewed ads that corresponded to their trial arm. They completed measures assessing message reactions after viewing each ad, after which they completed measures of susceptibility to vaping and smoking, vaping and smoking beliefs, and demographics. For the subsequent weeks of the trial (Visits 2 and 3), participants completed surveys with measures of susceptibility to vaping and smoking, vaping and smoking beliefs, and vaping and smoking behavior. Then, they viewed the same three ads from their trial arm and completed the message reactions items. At Visit 4, participants completed surveys assessing susceptibility to vaping and smoking, vaping and smoking beliefs, and vaping and smoking behavior (eFigure 1 in the Supplement).

**Primary outcome.** Susceptibility to vaping at Visit 4 was the primary trial outcome. Susceptibility prospectively predicts vaping behavior, including as a scaled score where higher values predict both greater initiation and current use of vapes. We assessed susceptibility with a 3-item susceptibility to vaping scale, similar to other studies. This scale assesses the extent to which adolescents are open to vaping, with a 4-point response scale ranging from “definitely not” (coded as 1) to “definitely yes” (coded as 4) (eTables 2 and 3 in the Supplement). We calculated a susceptibility score by averaging the 3 items, with higher scores representing higher susceptibility (Cronbach’s  $\alpha=.93$ ). Susceptibility was measured *after* ad exposure at Visit 1 to capture immediate ad impact and *before* ad exposure at Visits 2-4 to capture ad impact over time.

**Secondary outcomes.** The survey assessed several secondary outcomes hypothesized to elicit behavior change. Response scales for most secondary outcomes had five points, coded such

that higher scores represented a greater amount of the construct. For multi-item scales, overall scale scores were of the average of the items.

*Message reactions.* A single item assessed attention to the message and a 3-item scale assessed negative affect ( $\alpha=.83$ ). Message reactions were measured immediately following ad exposure. These measures were last assessed at Visit 3 because the ads were not shown at Visit 4.

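### The susceptibility model handles dropout using arm and earlier susceptibility only; leaving out the ad reactions recorded at Visits 1 to 3 can bias the Visit 4 contrast if the reaction links differ by arm

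*SAP*

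**What the plan says.** Under Primary analyses, the SAP assigns multiple imputation to missing predictors and "full information maximum likelihood to handle any missing data on outcomes". For the primary test, "the investigators will compare those in *The Real Cost* trial arms (combined) to the control arm", using a linear latent curve model with the intercept placed at the last visit and both growth factors regressed on the arm indicator. On scope: "The investigators will use a separate model for each of the study outcomes". No auxiliary variables, comparison of dropout by arm or reaction, or missing-data sensitivity analysis is named.

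Under Sample size and power, the SAP expects that "as many as 33% of participants will drop out of the study before week 3 follow-up". It says that FIML will use the repeated measures already observed on people who later leave.

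Higher attention and higher negative affect in the ad arms are stated hypotheses (SAP, Hypotheses). In the protocol (Measures), "Message reactions were measured immediately following ad exposure", at Visits 1, 2 and 3. Susceptibility is measured after the ads at Visit 1 and before them at Visits 2 to 4. The SAP's remark that reactions are assessed at 2 weeks only marks the last assessment and does not conflict with this.

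**The concern.** FIML gives valid estimates when dropout depends only on variables in the model. In the stated susceptibility model those are arm and earlier susceptibility. Reaction to the ads is a plausible further reason for leaving, and it is expected to differ by arm.

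The order of measurement matters. For someone who leaves after Visit 2 or 3, the last susceptibility score was taken before the last set of reactions, so it cannot fully stand in for them. The last information recorded before such a departure is outside the model.

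At stake is the primary contrast, read at the visit where dropout is greatest. If strong reactors leave and would have lowered their susceptibility, the benefit is understated. If they would have reacted against the message, it is overstated.

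**Working it through.** **Inputs from the SAP.** "The investigators plan to enroll 500 individuals per trial arm"; dropout up to 33%; two ad arms against one control arm; "The investigators will use a critical alpha of 0.05 in all statistical tests"; "With an estimated ICC=.7 (and thus a design effect of 2.4"); detectable d = 0.25.

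**The plan's own figures.** Design effect = 1 + (m − 1) × ICC. With m = 3, 1 + 2 × 0.7 = 2.4, which matches. With the four visits, 1 + 3 × 0.7 = 3.1. No power level is stated, so d = 0.25 can be neither confirmed nor refuted. It serves here only as a yardstick. After 33% dropout, 500 × 0.67 = 335 per arm remain, or 670 against 335.

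**Simulation of the stated model.** The documents give no figures for the links, so everything below is assumed.
- Susceptibility at four visits: person variance 0.7, residual variance 0.3 (ICC 0.7, total SD 1). The arm effect reaches −0.25 at Visit 4.
- Reaction at Visits 1 to 3: half its variance is a stable tendency u, and its mean is 0.5 SD higher in the ad arms.
- In the ad arms u shifts susceptibility by ρ·u·t, with t rising from 0 at Visit 1 to 1 at Visit 4.
- Dropout per interval is 1 − 0.67^(1/3) = 0.125 in every arm. In the ad arms its odds are multiplied by OR per SD of current reaction; in control OR = 1.
- N = 400,000, fitted with the SAP's linear latent curve model by FIML.

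Bias in the Visit 4 contrast (SD; negative means the benefit is overstated):

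| ρ | OR 1.5 | OR 2 | OR 3 |
|---|---|---|---|
| 0.15 | −0.011 | −0.019 | −0.028 |
| 0.3 | −0.024 | −0.039 | −0.056 |
| 0.5 | −0.039 | −0.065 | −0.089 |
| −0.3 | +0.025 | +0.036 | +0.055 |

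Against d = 0.25: 0.011/0.25 = 4%, 0.039/0.25 = 16%, 0.089/0.25 = 36%. With ρ = 0, or with OR = 1 in every arm, the bias is within 0.002. When the reactions are used to impute the missing scores separately by arm, it is within 0.003 throughout.

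**When the bias arises (ρ = 0.3).**
- Both links equal in all arms (OR 2): +0.001, so it cancels.
- Susceptibility link in all arms, dropout link in the ad arms only: −0.040.
- Susceptibility link in the ad arms only, dropout link in all arms: −0.038.
- Dropout driven by observed susceptibility alone: +0.001.
- OR 2 in the ad arms with 15% dropout instead of 33%: −0.017 instead of −0.039.

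**Timing of the reaction effect.** A second two-arm simulation (unstructured normal model, N = 300,000, 33% dropout per arm) set both links in the ad arms only, at 0.2 to 0.4 SD per SD and log-odds 0.5 to 1.0. Sizes of bias:
- effect fully present from Visit 1: 0.007 to 0.019 SD (3% to 8% of 0.25). A further two-arm run put this case at 0.005 to 0.02;
- effect growing linearly: 0.022 to 0.071 (9% to 28%);
- effect appearing only at Visit 4: 0.031 to 0.105 (12% to 42%).

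**Does adding the reactions cure it?** With covariances pooled over arms, only partly: 0.061 falls to 0.022, 0.105 to 0.039 and 0.042 to 0.016, so 36% to 38% remains. With covariances estimated separately by arm, the remainder is about 0.001 in this simulation and within 0.004 in the further run.

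**The case against.** The strongest reply is that the mechanism is assumed. No document links reaction to an ad with leaving. Exposure is three 30-second ads per session, payment rises to $15 for the final survey, and some 37% to 39% of ad-arm participants reported prior recall of the ads (Protocol, Table 1). The 33% is an upper allowance. All this stands, and it limits the claim to what can happen.

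The Visit 1 susceptibility score follows the reaction items, so an immediate effect of reaction is already in the model. This also stands, and it is why the lower end of the range is under 0.01 SD.

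Two further replies are fair. Separate models per outcome do not forbid auxiliary variables; the SAP simply names none. The protocol also commits to CONSORT reporting and cites a flow figure that is not shown, so a reader should not infer that dropout counts by arm will be missing. Neither reply meets the point: counts by arm say nothing about reactions, and the missing-data model as written does not use them.

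A reader might infer that a low-stimulus control arm cannot cancel the bias. The documents do not show that: if both links are the same in every arm, it cancels. Nor are arm totals a guide. Every biased case above had equal dropout by arm, and unequal dropout explained by earlier susceptibility is what FIML already handles.

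**Conclusion.** The point holds as a conditional weakness. Bias needs reactions to predict both leaving and later susceptibility beyond earlier susceptibility, with at least one link differing by arm. Its direction is unknown. Under assumed links its size runs from under 0.01 SD to about 0.09 to 0.10 SD, against d = 0.25. The low end applies if the reaction effect is already in the post-ad Visit 1 score, the high end if it grows or appears late and the links are strong.

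A reader might go further and conclude that the ads do drive participants out, or that the primary result is biased by a known fraction. The documents support neither, since they report no relation between reaction, dropout and susceptibility. What they do support is that the trial records a plausible predictor of dropout at the right moments and the stated model does not use it, although using it is cheap.

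**What to change.** In the SAP, Primary analyses, enter negative affect and attention at Visits 1 to 3 as auxiliary (saturated-correlate) variables in the FIML growth models for susceptibility and the other Visit 4 outcomes. Let covariances differ by arm, through multi-group FIML or multiple imputation done separately by arm. The arm contrast stays as planned. The simulations used a single reaction measure; attention is included because it is recorded at the same moments.

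Tabulate non-return at Visits 2, 3 and 4 by arm and, within arm, by reaction at the preceding visit. Base any caution about the Visit 4 conclusion on two things: whether the relation of reaction to dropout differs by arm, and whether the estimate changes when the auxiliaries are added. The second is needed because bias also arose (−0.038) with the same dropout relation in all arms. Arm totals alone should not decide.

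The cost is SAP wording, a few lines of model code and one table. The model is larger, has more parameters because covariances are arm-specific, and may need convergence checks. No new data are needed. If the primary analysis has already been run, the same model can be reported beside it as a sensitivity analysis.

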**Impact of The Real Cost Vaping Prevention Advertisements on Adolescents**

**Protocol**

**NCT #04836455**

**Version Date: 5/27/2021**

## Participants

We recruited adolescents living in the United States (US) from online panels administered by Qualtrics. Eligibility criteria were: aged 13 through 17 years, able to read and speak in English, able to take an online survey in English, and susceptible to e-cigarette use as shown by an answer of 2 or greater on any of five e-cigarette susceptibility items. The susceptibility items assessed the extent to which adolescents were open to vaping, with a 4-point response scale that ranged from “definitely not” (coded as 1) to “definitely yes” (4).

Our target sample size was 1,500, which accounted for up to 33% of participants dropping out during the trial. With an estimated intraclass correlation of .70, the trial had power to detect an effect size of  $d=.25$  or larger between intervention arms (combined) and the control arm.

Recruitment took place from September to November 2021. Legal parents or guardians provided informed parental consent online, and adolescents provided assent online before beginning the surveys. Of the 1,708 adolescents who met inclusion criteria, 151 declined to participate and 43 were screened but unable to enroll because the study quota had been met (Figure 1). This trial was approved by the University of North Carolina Institutional Review Board and is registered at [clinicaltrials.gov](https://clinicaltrials.gov/ct2/show/NCT04836455), identifier NCT04836455 (<https://www.clinicaltrials.gov/ct2/show/NCT04836455>). This paper follows CONSORT reporting guidelines for RCTs.

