## Procedures

*Trial design and protocol.* We conducted a three-arm RCT with parallel assignment. Adolescents participated in four weekly online visits over a three-week period, completing a survey at each visit. Exposures to campaign ads occurred at Visits 1, 2, and 3. At the start of the

trial (Visit 1), participants were randomized to see a series of ads from one of two FDA *Real Cost* vaping prevention ad trial arms (health harms or addiction) or to a control arm (investigator-created neutral videos about vaping). Qualtrics software used simple randomization based on a single allocation ratio. Participants were randomized without replacement to one of the three trial arms using the Qualtrics randomizer. In each trial arm, participants viewed the same three ads per session, in a random order, corresponding to the trial arm they were assigned. Participants were told they were going to view three short ads, but received no information on the content or number of arms. The research team was not blinded after assignment because interventions were administered online.

At each of the visits (Visits 1 – 4), participants completed surveys reporting primary and secondary outcomes. Participants received incentives in the form of points for taking the surveys, with a total cash equivalent of \$35 after completing the trial (\$5 for the first and second surveys, \$10 for the third survey, and \$15 for the final survey). A pilot study with 51 participants was conducted prior to the trial to test trial procedures.

*Intervention messages.* Participants in both intervention trial arms viewed three 30-second ads from the *Real Cost* campaign, corresponding to one of the two major themes of the campaign. Those in the health harms trial arm viewed ads about toxic substances and lung damage, while those in the addiction trial arm viewed ads about consequences of nicotine addiction. Those in the control arm viewed three 30-second investigator-created neutral videos about vaping consisting of black text on a white screen with a narrator reading the text. The content of these ads included product definitions, farming practices, and manufacturing practices adapted from Wikipedia and other sources (see the Table 1).

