*Vaping outcomes.* Three-item scales assessed cognitive elaboration ( $\alpha=.92$ ), social interactions ( $\alpha=.94$ ), vaping health harm risk beliefs ( $\alpha=.92$ ), vaping addiction risk beliefs ( $\alpha=.89$ ), and vaping attitudes ( $\alpha=.91$ ). Participants reported the number of days they vaped over the past 7 days at each visit. These outcomes were measured *after* ad exposure at Visit 1 and *before* ad exposure at Visits 2-4, except for days vaped which was always measured before ad exposure.

*Smoking outcomes.* Single items assessed smoking health harm risk belief, addiction risk belief, and smoking attitude. Susceptibility to smoking was assessed with a 3-item scale ( $\alpha=.95$ ). Participants reported the number of days they smoked over the past 7 days at each visit. We chose to retain the continuous measures of number of days vaping and smoking rather than dichotomizing these outcomes (as proposed in our trial registration) because we found substantial variability in number of days that these products were used.

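### A precision gain left unused, not an error: the primary model conditions on arm alone although vaping days are recorded before the first ads

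*SAP*

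**What the plan says.** SAP, Primary analyses: after a linear trajectory is fitted with the intercept at the last time point, "the investigators will regress the latent intercept and slope factors for each outcome on an indicator of random assignment". No other regressor is named. Current-vaper status appears only among the exploratory moderators.

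Protocol, Procedures: "Qualtrics software used simple randomization based on a single allocation ratio", so no baseline factor enters through stratification.

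Protocol, Measures: at Visit 1 "each participant reported vaping and smoking behaviors in the survey, then viewed ads that corresponded to their trial arm". The susceptibility scale was taken after "ad exposure at Visit 1 to capture immediate ad impact", and before the ads at later visits. The other vaping outcomes follow the same timing, "except for days vaped which was always measured before ad exposure".

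Protocol, Participants: to be eligible an adolescent had to be "susceptible to e-cigarette use as shown by an answer of 2 or greater on any of five e-cigarette susceptibility items". Those items were therefore answered before randomization. The documents do not say whether the item answers were kept and linked to the trial data.

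**The concern.** In a four-wave growth model it is natural to assume that the first wave serves as a baseline. Here it does not, because the first susceptibility score already contains the effect of the first ads. Simple randomization adds no baseline information, and the growth factors are regressed on arm alone. The primary estimate therefore uses no pre-treatment information about the participant.

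One pre-exposure variable is certain to be in the data: Visit 1 days vaped. If it is correlated with susceptibility, including it removes some between-person variance from the arm contrast. In a linear model this does not change the effect being estimated. What is at stake is precision in the primary comparison, and in the health-harms versus addiction comparison, which the SAP calls exploratory and not powered. Validity is not at stake.

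**Working it through.** **The plan's own figure.** The SAP gives 500 per arm, up to 33% dropout, ICC .70, design effect 2.4 and d = .25, with no power level. The design effect is 1 + (3 − 1) × .70 = 2.4, which corresponds to three measures. With two-sided alpha .05 (sidedness assumed) and 2:1 allocation:
- 1,500/2.4: SE = √(2.4/500 + 2.4/1,000) = .0849. The 80% detectable d is 2.802 × .0849 = .238, and power at .25 is .838.
- Completers only, no design effect (335 v 670): power .962.
- Completers/2.4: detectable d .290, power .674.

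Several readings support d = .25, but without a stated power level it cannot be reproduced uniquely.

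**Inputs for the check.** From the documents: ICC .70, 33% dropout, 1,000 v 500, FIML, four visits. Assumed: dropout of 11% after each of Visits 1 to 3; r, the within-trial correlation of the covariate with the observed Visit 1 susceptibility score; and either a constant correlation or one decaying by .9 per visit.

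**Method.** Code time −3, −2, −1, 0. Outcome covariance is V = .70J + .30I (J all ones, I the identity). Adjusted covariance is V − cc′, with c_t = r (constant) or r × .9^(t−1) (decay, t the visit number). Sum the information X′V⁻¹X over participants with 1, 2, 3 or 4 visits observed (.11, .11, .11, .67) and invert. The first diagonal element v is the per-person variance of the Visit 4 intercept, and SE = √[v(1/1,000 + 1/500)].

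**Unadjusted.** v = 1.065; SE = √(1.065 × .003) = .0565; 95% half-width 1.96 × .0565 = .111 SD; power at d = .25 is Φ(.25/.0565 − 1.96) = .993.

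**Adjusted.**

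| r | v, constant | SE reduction | v, decay | SE reduction |
|---|---|---|---|---|
| .1 | 1.055 | 0.5% | 1.060 | 0.2% |
| .2 | 1.024 | 1.9% | 1.044 | 1.0% |
| .3 | .972 | 4.4% | 1.018 | 2.2% |
| .5 | .807 | 13.0% | .933 | 6.4% |

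**In participants.** 1,500 × (v unadjusted / v adjusted − 1) gives 1,500 × (1.0649/1.0596 − 1) ≈ 7 at r = .1 with decay, and 1,500 × (1.0649/.9725 − 1) ≈ 143 at r = .3 constant.

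**At r = .3.** The half-width becomes .106 to .108 and power .995 to .996. For health harms versus addiction (500 v 500), detectable d goes from 2.802 × √(1.065 × .004) = .183 to .175–.179.

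**Sensitivity.**
- Random slopes (variance .03, diverging from Visit 1): v = 1.404 unadjusted, so SE = √(1.404 × .003) = .0649 and power is Φ(.25/.0649 − 1.96) = .971. The reduction at r = .3 is 3.3% (constant) or 1.7% (decay); at r = .5 it is 9.6% or 4.8%.
- Timing of dropout and ICC .5 to .8: at r = .3, 4.2–4.8% (constant) and 2.1–2.4% (decay).
- Meaning of r = .3: if it is the correlation with the latent intercept, the reduction is 3.0–3.1% with 33% dropout and 3.5% with none. If it is with the observed score and nobody drops out, it is 5.1%.

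**Range restriction, screening score.** Entry truncates this score from below. With r′ = ru/√(1 − r² + r²u²), an unselected r of .5 becomes .5 × .603/√(.75 + .25 × .603²) = .33 if the upper half qualifies, and .5 × .514/√(.75 + .25 × .514²) = .28 if the upper 30% does. Both selection fractions are assumed.

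**The case against.** The strongest case against raising this is that nothing is broken. A randomization-based unadjusted analysis is a legitimate choice, and moving power from .993 to .996 will not plausibly change a conclusion. The value of r is also undocumented. The statement that "higher values predict both greater initiation and current use of vapes" is cited background, not a correlation in this screened sample. The remark that "we found substantial variability in number of days that these products were used" concerns spread, not association, and was made after data were seen. A covariate with missing values would bring imputation into a primary test that could otherwise run on FIML alone. All of this stands. It limits the size of the point, but does not remove a gain that is nearly free.

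A reader might infer more than the documents support:
- **That the arm-only test is biased or underpowered.** Randomization protects the test. The low-power reading (.674) divides completers by the repeated-measures design effect without counting the repeated measures; 335 × 3/2.4 in control, with twice that in the combined arms, gives .987.
- **That adjustment would repair dropout bias.** It helps only where dropout depends on the measured baseline, differently by arm, and nothing in the documents shows that. In an illustrative simulation with arm-specific dropout driven by the underlying trait, bias at r = .3 was −.050 SD unadjusted and −.049 adjusted.
- **That the screening score promises a large gain.** At r = .7 the simple formula 1 − √(1 − r²) gives 28.6%. But entry restricts the score's range, and retention and linkage of the answers are not documented.

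**Conclusion.** The point holds as a free improvement. The SAP's primary model leaves a known pre-exposure variable unused. For Visit 1 vaping days, the only covariate certain to exist, the assumed range r = .1 to .3 gives an SE reduction of about 0.2% to 4.4%. The low end is negligible. About 5% to 13% needs r = .5, which is plausible only for the screening score and only if its answers are usable. These figures rest on the plan's ICC and dropout and on efficient use of partial data; r is a reviewer's assumption throughout. The arm-only test remains valid with about 99% power at d = .25 (about 97% with the random-slope variance tried), so the return is a slightly narrower interval.

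**What to change.** For the susceptibility-to-vaping model, and for its health-harms versus addiction version, state in the SAP that the latent intercept and slope are regressed on arm plus Visit 1 pre-exposure days vaped, entered in a stated form such as a linear term. Add the mean of the five screening items if the answers were kept and linked. State that Visit 1 susceptibility is not a covariate because it follows exposure. Keep the arm-only model as a sensitivity analysis.

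The protocol text already describes recruitment and scale reliabilities in the past tense. If outcomes have been examined, leave arm-only as primary and report the adjusted model as a labelled sensitivity analysis, since a covariate chosen after seeing results is less credible.

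The cost is one or two sentences, one or two covariates and one extra model run. Days vaped needs no new data, and missing covariate values fall under the multiple imputation the SAP already plans for predictors.
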